can see how his blood hormones change at different times. The experimenter will draw blood from the subject's arm three times: 1) 30 minutes after your arrival at the high-performance electrical neuroimaging laboratory, 2) one 2 and 30mn later and 3) again an hour later. About 1 teaspoon of blood will be taken each time.

- The subject will also be asked to provide saliva samples during the study at the same three times: 1) 30 mn after your arrival at the high-performance electrical neuroimaging laboratory, 2) one 2 and 30mn later and 3) again one an hour later. About 1 teaspoon of saliva will be taken each time. We ask the subject to provide saliva samples so that we can see how the samples are related to behavioral tasks and how the subject is feeling at different times in the study.
- The subject will watch a 2-hour-long relaxing movie in a quiet and relaxing environment.

Two hours after the subject takes the pill (drug or placebo), the following will occur:

- The subject will do the exact same behavioral visual task on a computer . Control subjects will perform the same tasks at the same time, except they will not take any pills.
- The subject will complete the same questionnaires again.
- The subject will wait for 30 minutes in a relaxing and quiet environment.
- The subject will be given a parking voucher or \$5 for public transportation and a \$60 monetary compensation for participating in the study.

Estimated Duration of Visit: Between 4 Hours and 4 ½ hours

In the event suicidal ideation or similar events take place during the study, the subject will be removed from the study and referred to the appropriate clinical resources.

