C.2.6. Neurosteroid Analyses: To compare ALLO results with Sripada et al.'s 2013, basal serum levels will also be taken (once prior to drug administration and once two hours after oral administration of the drug study) and analyzed using a gold-standard in the literature: a gas-chromatographic mass-spectrometric (GC-MS) approach. Serum levels of pregnenolone, progesterone, 5alpha-DHP and ALLO and pregnanolone (ALLO's steroisomer and GABA-active) will be measured. As in Majewaska et al (2014), saliva samples will be analyzed using the same gold standard GC-MS approach in ALLO literature i.e., a method that allow for accurate measurement in the femtomolar range of specific neurosteroids. We will ensure that participants will refrain from smoking, eating, drinking alcoholic, caffeinated, or juicy beverages, and brushing teeth at least one hour before the first saliva sample and between saliva samples.

C.2.7. General Statistical approach:

Demographic and self-report psychological measures: Statistical analyses for demographic and self-report measures will be computed using SPSS software. Prior to inferential analyses, descriptive statistics, including distributions, means, standard deviations, skewness, and kurtosis will be generated. Data will also be examined for the pattern and mechanism of missing data. Continuous data will be tested for normality and homogeneity of variance. Potential differences between the study groups in terms of demographic and behavioral measures will be explored using multivariate analysis of variance (MANOVA) or appropriate non-parametric tests as appropriate. The overall significance level for these analyses will be at 5% using two-tailed tests and effect sizes and confidence intervals will be reported. In addition, scores at self-report questionnaires will be analyzed via a 2 (Drug Type: PREG 400mg, or PBO) x 2 (time: before, after) repeated measures ANOVA to assess for main effects and interaction effects.

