Behavioral paradigms: Statistical analyses will be computed using SPSS software. Reaction times and performance data will be screened and any outliers will be removed based on each participant's trial-by-trial data. A trial will be removed if it differed by 3 standard deviations above or below the participant's mean. Prior to inferential analyses, descriptive statistics, including distributions, means, standard deviations, skewness, and kurtosis will be generated. Data will also be examined for the pattern and mechanism of missing data.

• For the *body language* paradigm: A 2 (Drug Type: PREG 400mg, or PBO) x 2 (type of stimuli: social, non-social) x 2 (nature of the stimuli: threat, non-threat) repeatedmeasures ANOVA will be performed on the reaction times and valence ratings to assess for main effects and interaction effects. P values, confidence interval, and effect sizes will be reported.

C.2.6. Power Analysis: Using G* power calculation software (Version 3.1.9.2; © Franz Faul, Edgar Erdfelder, Albert-Georg Lang, and Axel Buchner, 2006, 2009) for a within-between interaction in a repeated measures ANOVA, a total sample size of 36 for three groups will yield 95% power to detect a significant difference, with alpha = 0.05 and an effect size Cohen's *d of* 0.35 in the present project.

Note: The hormone tested in saliva and blood have the same origin from adrenals glands and gonads. Here we want to establish a correlation within the same subjects among the levels of the same neuro-active steroid determined in the blood and the saliva. We expect the hormone levels measured in saliva and in blood to be different in amount but to correlate.

Saliva samples will be analyzed using the same gold standard GC-MS approach in ALLO literature i.e., a method that allow for accurate measurement in the femtomolar range of specific neurosteroids. We will ensure that participants will refrain from smoking, eating, drinking alcoholic, caffeinated, or juicy beverages, and brushing teeth before each saliva sample.

7. Special Precautions:

Pregnenolone side effects, danger, risk, and the harm it can cause

Overstimulation and insomnia -

Irritability, anger or anxiety -

Acne can occur due to the probable conversion of this hormone into androgens

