A researcher will be present with participants during the duration of the experiment. While participants are in a separate room sheltered, researchers will monitor participants' wellbeing via cameras and microphones within this room. Participants will have the ability to communicate with researchers through these microphones and may opt out of participation at any time. Participants will also be provided with the IRB's contact information on the consent form, and we will contact IRB should any adverse effects occur.

Regarding pregnenolone's side effects: Subjects will be directed to call a member of the study team if they believe they are experiencing any side effects within the 12 hours following the end of the study.

13. Payment:

Participants will receive the \$60 monetary compensation (Internal Fundings/No Fund) for their participation in the entire study. If participants should decide to opt out of participation after the beginning of the study, their participation would be pro-rated (\$15 per hour).

14. Informed Consent:

We are asking to waive first consent form to do a brief phone interview and see whether the participants are eligible. Then the participants will come to the University of Chicago and read, understand and sign the written consent form attached in this IRB application. Participants must acknowledge understanding of procedures, risks, and benefits by signing this consent form before the study can proceed.

15. Confidentiality:

De-identified data will be stored in locked drawers or cabinets or on password-protected computers within the HPEN laboratory or on password protected University of Chicago server, such as UChicago Box. Data may be used in publications, but no personally identifiable information will be disseminated outside of researchers included in this protocol.

16. Recruiting Methods:

Subjects will be recruited via Flyers posted on Campus, sona or websites, such as craigslist.

17. Primary Physician Notification:

[name], M.D.

18. Anticipated Coordination between Inter-Departmental Faculty:

[name]., [name]., and [name]. are all members of the Department of Psychiatry and Behavioral Neuroscience. [name] is the Director of the Center for Cognitive and Social Neuroscience. These researchers will coordinate extensively on this project.

19. Pregnancy Test: N/A. The present research only includes male participants.

20. Drug Test:

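### The before/after questionnaire ANOVA defaults to men who have a post-dose score, and the plan names no analysis set or handling for men who do not

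*Combined protocol and SAP*

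**What the plan says.** **Analysis.** C.2.7 says that "scores at self-report questionnaires will be analyzed via a 2 (Drug Type: PREG 400mg, or PBO) x 2 (time: before, after) repeated measures ANOVA", and that "Statistical analyses for demographic and self-report measures will be computed using SPSS software". On the level of the tests: "The overall significance level for these analyses will be at 5% using two-tailed tests".

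**Missing data.** The only provision is "Data will also be examined for the pattern and mechanism of missing data". It stands in C.2.7 for the self-report measures and again for the behavioural paradigms. No analysis set, imputation, likelihood-based model, sensitivity analysis or exit allowance is named.

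**Timing.** Section 7 (Research Methods) describes one visit. The second round of task and questionnaires is introduced by "Two hours after the subject takes the pill (drug or placebo), the following will occur". There is one post-dose questionnaire time.

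**Routes to a missing score.** Section 12 (Monitoring of Safety) says that participants "may opt out of participation at any time". Section 13 (Payment) adds: "If participants should decide to opt out of participation after the beginning of the study, their participation would be pro-rated", at $15 per hour against $60 for completion. Section 7 also removes a man from the study if suicidal ideation or a similar event occurs.

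**Overlap with outcomes.** Section 7 (Special Precautions) lists "Irritability, anger or anxiety" among the side effects. C.2.3 includes the Hospital Anxiety and Depression Scale, given before and after the drug, and Hypothesis 2A concerns depressive symptomatology.

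**The concern.** Randomisation protects the comparison of all men allocated to each arm. A model that needs both scores compares a subgroup formed after dosing. If the reason for a missing post-dose score is related to how the man felt on the drug, the contrast among those who remain differs from the randomised contrast.

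Several features make this possible. The only post-dose score comes two hours or more after the pill, so an effect can appear before anything is recorded. Pro-rated pay reaches the full $60 at four hours (4 × $15), so there is little financial reason to stay. Men with untreated major depressive disorder are eligible, and removal for suicidal ideation is tied directly to mood. At stake is the direction and size of the PREG–placebo contrast on anxiety, depression and loneliness scores.

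**Working it through.** **The plan's own figures.** The plan gives no exit rate or missing-data figure. The nearest number is the sample size in C.2.6 (Power Analysis): 36 in three groups, 95% power, effect size 0.35. Taking 0.35 as Cohen's f, two time points and an assumed correlation of 0.5, the noncentrality is f²·N·m/(1−ρ) = 0.1225 × 36 × 2 / 0.5 = 17.64 on 2 and 33 df. Power is 0.9575, so the figure reproduces, though the text labels it Cohen's d. It carries no allowance for missing scores.

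**Inputs.** 112 per arm is from section 7 (Research Methods). Everything else is assumed: a fraction q of PREG men is missing and none on placebo; leavers' change is D SD worse than that of PREG men who stay; the all-randomised effect is zero.

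**Bias.** The stayers' mean differs from the full-arm mean by q × D, in favour of PREG. The table takes the SD of the change score as the unit; this equals the SD of a single score when the before-after correlation is 0.5. Type I error is two-sided, nominal 0.05, by normal approximation.

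| q (PREG men missing) | Bias, D = 0.5 / 1 / 1.5 | Type I error |
|---|---|---|
| 2% (about 2) | 0.010 / 0.020 / 0.030 | 0.051 / 0.053 / 0.056 |
| 5% (about 6) | 0.025 / 0.050 / 0.075 | 0.054 / 0.066 / 0.086 |
| 10% (about 11) | 0.050 / 0.100 / 0.150 | 0.065 / 0.113 / 0.194 |
| 20% (about 22) | 0.100 / 0.200 / 0.300 | 0.109 / 0.292 / 0.562 |

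**Dependence on the correlation.** Now let leavers be 1 SD worse than the all-randomised mean of zero, with the SD of a single score as the unit. Stayers then show a benefit of q/(1−q): 0.053 at 5% and 0.111 at 10%. The standard error is √(2(1−r)) × √(1/(112(1−q)) + 1/112). At r = 0.7 it is 0.105 and 0.106. The chance of a significant result favouring PREG is 1 − Φ(1.96 − bias/SE) = 7.2% and 18.0%, against a nominal 2.5%. At r = 0.5 the figures are 5.8% and 12.5%; at r = 0.9 they are 13.8% and 44%.

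**Smaller trial.** Section 9 and C.2.6 (Power Analysis) state 36 subjects in total, against 224 plus 12 controls in section 8. At an assumed 12 per arm, one missing PREG man gives a bias of 0.04 to 0.125 SD and type I error of 0.051 to 0.060. Three give 0.125 to 0.375 SD and 0.059 to 0.136.

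**What baseline adjustment gains.** With complete data, the ratio of its standard error to that of the change-score analysis is √(1−r²)/√(2(1−r)) = √((1+r)/2). At r = 0.7 this is √0.85 = 0.922, about 8% smaller. It is 0.866 at r = 0.5 and 0.975 at r = 0.9.

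**What baseline adjustment does not fix.** I simulated 112 per arm, r = 0.7 and 11 PREG exits, with leavers 1 SD worse than the zero all-randomised mean only in the unseen score. The bias is about 0.11 SD under both the change-score analysis and baseline-adjusted regression, which stands in here for the common-baseline mixed model. The chance of a significant result favouring PREG rises slightly, from about 17–18% to about 20%, because the same bias is divided by a smaller standard error.

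**The case against.** The strongest reply is that this may hardly arise. There is a single visit, most of the wait is a relaxing film, and the questionnaires are repeated soon after the two-hour mark. The rationale section reports minimal side effects for 25–500 mg/day, and the background cites a single 400 mg dose associated with lower self-reported anxiety. The side-effect list gives no frequency or timing. All of this stands: the exit rate is unknown and may be negligible, and the direction of any bias is not established.

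The calculation is also one-sided by construction: every loss is on PREG, and every leaver is worse. Deletion applies to both arms, and it favours PREG only if losses differ by arm or by reason.

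A reader might infer more than the documents support:

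- **That the protocol expects exits.** It gives an ordinary right to withdraw and a payment rule, with no anticipated rate.
- **That deletion of incomplete cases is a stated rule.** It follows from the method; the text does not state it.
- **That the body-language ANOVA loses the same men.** That model has drug, stimulus type and threat as factors and no time factor, and the plan does not say which session's data enter it.
- **That a mixed model alone removes the bias, or that the remedy changes nothing without exits.** The working shows neither is so.

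The objection leaves one gap untouched: examining the pattern of missing data, with no consequence specified, is not a method for handling it.

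**Conclusion.** The concern holds in a limited form. As written, the questionnaire analysis is a completers' analysis by default, with no all-randomised set and no specified response to missing post-dose scores. Losses related to arm and outcome are possible by two documented routes, opt-out and removal.

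On assumed one-sided loss with leavers 1 SD worse, the bias is small at 2–5% (about 0.05 SD at 5%) and about 0.1 SD at 10%. These sizes rest on 112 per arm and on exit rates and leaver differences that the documents do not supply. The text does not support saying that the PREG result will be biased, only that the plan could neither detect nor bound such a bias. Change is worthwhile because it is cheap, because a score not collected at exit cannot be recovered later, and because the better model improves precision even with complete data.

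**What to change.** 1. **Collect the score.** Add one line to the visit procedures: a man who opts out after the pill is invited to complete the post-dose questionnaires before leaving, and the time since the pill is recorded.
2. **Specify the set and model.** Analyse all randomised men in their allocated arm with a linear mixed model that uses every available score, assumes a common baseline mean, and takes the post-dose drug difference as the contrast, in place of the change-score ANOVA. SPSS, already named, can fit it. This handles loss related to baseline; items 1 and 3 address loss related to the unseen score.
3. **Report and stress-test.** Tabulate missing post-dose scores and their reasons by arm, including removals for suicidal ideation or similar events. Add one sensitivity analysis that shifts missing PREG post-dose scores unfavourably by 0.5 and 1 SD.

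**Cost.** Analysis wording, one procedural line and one extra table. Exit scores will come at varying times after the pill, so they are not fully comparable with the scheduled ones. The conflicting totals (36 against 224 plus 12) should be reconciled separately, since they decide how much a single missing man matters.

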The goal of the proposed research, which is based on prior human and animal work, is to test a proof-ofconcept that acute oral administration of PREG reduces PSI in male adults (aged 21-80) high in PSI. Validated self-report measures (e.g., depression, anxiety, objective social isolation, life satisfaction) will also be used to examine changes in symptom severity and subjective feelings. The long-term objective of this project is to advance the use of PREG at remediating the protracted reduction in the neurosteroid, ALLO in individuals high in PSI and thereby reduce PSI and improve social withdrawal. The proposed project will employ a randomized between-subjects

design, where a validated behavioral paradigm on social threat attention, intention understanding, and perception of others will be combined with validated measures of depressive symptomatology in male adults (aged 21-80) high in PSI.

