
Rationale for selected dose range in the present project: Here, 224 subjects high in PSI will be randomized to a single oral dose of PREG 400mg (n=112), or placebo (PBO, n=112) to ascertain dose of administration. The rationale for the selected dose range is the following: First, clinical trials showed that PREG 25–500 mg/day is safe and well tolerated in humans. Second, Sripada and colleagues made the compelling basic science discovery that a single dose (400mg) of PREG up-regulates ALLO in young adults (See Fig. 1) and reduces activation of brain areas underlying negative emotions processing.

Steroid (pg/ml)	Placebo (n=15)		Pregnenolone Group (n=16)			
	Baseline (Mean ± SD)	Endpoint (Mean ± SD)	Baseline (Mean ± SD)	Endpoint (Mean ± SD)	ï	р
Pregnenolone	1378.8 ± 579.1	1190.8 ± 468.5	1238.0 ± 378.7	3943.6 ± 696.3	12.3	<.001
Allopregnanolone	114.3 ± 49.6	118.1 ± 76.5	112.3 ± 40.9	802.2 ± 280.7	10.2	<.001
Pregnanolone	470.6 ± 200.8	490.5 ± 135.6	352.0 ± 106.6	517.4 ± 96.2	3.2	.004

Fig. 1. Steroid and metabolite levels in Sripada et al.'s 2013. *T-tests were conducted on change scores (steroid levels at endpoint minus steroid levels at baseline). Pregnenolone group received an acute, oral dose of PREG 400mg.

Based on pharmacokinetic data in humans, we expect the peak serum concentration of ALLO to occur approximately 2 hours after acute, oral administration of PREG 400mg. Saliva levels will be measured at the following 3 time points: -0.5, 2.0, 3.0 to provide various measures and correlations with behavioral tasks and correlations with serum levels.

4. Aims & Hypotheses:

Specific Aim 1: Assess PREG on levels of ALLO in a dose-finding design. Relative to PBO, PREG will dose-dependently increase and normalize ALLO levels in individuals high in PSI such that it will be comparable to Matched Healthy Controls (MHC) (Hypothesis 1A).

Specific Aim 2: Examine PREG on attentional bias to social threats and depressive symptomatology in individuals who are high in PSI. Relative to PBO, PREG will reduce depressive symptomatology and attentional bias to social threats and improve intention understanding and perception of others in individuals high in PSI (Hypothesis 2A). Hypothesis 2B: In PSI and MHC, depressive symptomatology and attention to social threats will correlate negatively with ALLO levels.

5. Duration of the study: The total duration of the entire study on campus is between 4 and 4 $\frac{1}{2}$ hours maximum.

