7. RESEARCH METHODS

The Approach

This project will comprise a randomized, placebo- controlled, between-subjects design, where we will couple a validated behavioral paradigm on attention to social threats with an acute pharmacological challenge with oral pregnenolone (PREG) or placebo (PBO) in subjects high in PSI and test behavioral responses and neuro-active steroid levels *prior and after study oral drug administration*. In the present project, 224 PSI subjects will be randomized to a single oral dose of PREG 400mg (n=112), or placebo (PBO, n=112) to ascertain dose of administration. In this project, participants will attend a single laboratory visit. During this single session, behavioral responses and subjective feelings will be tested at two time points (once before and once after). Neuro-active steroids will be measured from blood and saliva at several points to ascertain they correlate. A group of Matched Healthy Controls (MHC) who are low in PSI (n=12) and will not receive PREG but will otherwise complete all questionnaires of the study. Participants will be recruited from the University of Chicago and in the community.

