All participants must be 1) Male; 2) Aged 21-80 (inclusive); 3) High in PSI (PSI > 42, except for controls who should have a score < 42); 4) Do not meet Mini-International Neuropsychiatric Interview (M.I.N.I) criteria for psychiatric illness (except untreated major depressive disorder); and 5) BMI <30 (as ALLO levels are higher in obese than non-obese individuals). Key Exclusion Criteria: Female, as ALLO levels vary as a function of the menstrual cycle; 2) Aged < 21 or > 80; 3) Low in PSI (PSI < 42, except for controls)); 4) meet M.I.N. I criteria for psychiatric illness, besides untreated major depressive disorder; 5) Uncorrected vision; 6) Medical history of cancer; 7) Medical history of condition that might be made worse by exposure to estrogen or testosterone; 8) Recent steroid use; 9) Currently taking psychotropic medication; 10) History of seizures, neurological disorders; 11) History of TBI with loss of consciousness and/or with current cognitive impairment related to TBI; 12) Under hormonal therapy (including, but not limited to, testosterone); 13) Any unstable medical illnesses; 14) Lifetime history of bipolar disorder, schizophrenia, or psychotic disorder; 15) Current or recent (past 3 months) substance abuse or dependence; 16) Currently taking any medications that have/may have unfavorable interactions with Pregnenolone; 17) History of irregularities of heart rhythm, or heart palpitations; 18) obesity (defined as BMI>30); 19) illegal drug use as determined by urine drug screen.

Rationale: The recruitment and random assignment of young adults high in PSI to the PREG and PBO conditions allow us to ascertain the effects of PREG on PSI, depressive symptoms, and attentional biases for social threats. In addition, the recruitment of participants between the ages of 21 and 80 years will allow us to compare emotional and neurobiological findings across groups without the confounder of age effects.

Upon receipt of written consent, subjects will fill out self-report questionnaires and undertake practice on our behavioral paradigm.

During the visit, the following will occur:

- The subject will complete several questionnaires, including questions about perceived social isolation and questions about his mood.
- The subject will do a visual task on a computer.
- If the subject has low perceived isolation, the study drug will NOT be given.
- The subject will be asked to provide blood samples throughout the visit so that we

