Headaches are possible with high dosages or low dosages used over several days or weeks. Possible scalp hair loss if used daily for prolonged periods. Pregnenolone converts into DHEA, which in turn converts into testosterone and possibly on to DHT. It can also be converted into progesterone.

Irregularities of heart rhythm, Heart Palpitations, even on as low a dose as 5 mg. This can be serious in the elderly or those with heart rhythm disturbances.

Unknown effects on the thyroid gland or other organs and tissues.

Special Precautions & Warnings:

Pregnancy and breast-feeding: Although there is not enough known about the use of pregnenolone during pregnancy and breast-feeding, we'll avoid this risk by testing male participants only.

Hormone-sensitive condition such as breast cancer, uterine cancer, ovarian cancer, endometriosis, or uterine fibroids might have an interaction with pregnenolone: We'll exclude participants with any history of condition that might be made worse by exposure to estrogen.

8. Participants:

We will recruit 224 men (between 21 and 80) high in PSI and 12 Matched Healthy Controls (MHC) who are low in PSI.

9. Type and Number of Experimental Subjects:

We expect to collect data from a total of 36 subjects (between 21 and 80).

10. Potential Risks and Benefits:

The study will offer no direct benefits (besides monetary benefits and potential improvement of sexual desire) to participants. The questionnaires and behavioral task also present minimal risks, which may include boredom and fatigue from looking at pictures for a few minutes and anxiety or discomfort or distress related to responding to questionnaires.

11. CONTRAINDICATIONS:

• Estrogens interacts with PREGNENOLONE

Taking estrogen along with pregnenolone might cause too much estrogen to be in the body.

Some estrogen pills include conjugated equine estrogens (Premarin), ethinyl estradiol, estradiol, and others.

Progestin interacts with PREGNENOLONE

Progestins are a group of hormones. Taking other hormones along with progesterone pills might cause too much hormones in the body. This could increase the effects and side effects of hormone pills.

• Testosterone interacts with PREGNENOLONE

Taking pregnenolone along with a testosterone pill might cause too much testosterone in the body. This might increase the chance of testosterone side effects.

12. Monitoring of Safety:

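### Self-report outcomes: name Drug x Time, or better a baseline-adjusted ANCOVA, as the treatment test; the pre-dose score is already collected and the precision gain is probably modest

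*Combined protocol and SAP*

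**What the plan says.** Section C.2.7 (General Statistical approach, demographic and self-report measures) analyses the questionnaire scores by a "2 (Drug Type: PREG 400mg, or PBO) x 2 (time: before, after) repeated measures ANOVA to assess for main effects and interaction effects". No effect in that model is named as the test of treatment, and no analysis adjusts for the pre-dose score.

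These analyses carry two claims. Section 2 (Purpose) sets out to show that "acute oral administration of PREG reduces PSI in male adults (aged 21-80) high in PSI". Hypothesis 2A, under Aims & Hypotheses, states: "Relative to PBO, PREG will reduce depressive symptomatology and attentional bias to social threats".

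The pre-dose score is available. Section 7 (The Approach) says that "subjective feelings will be tested at two time points (once before and once after" the drug or placebo, and the visit procedures say of the post-dose period: "The subject will complete the same questionnaires again". Section C.2.3 lists the repeated scales: UCLA-R, objective isolation, Hospital Anxiety and Depression, and life satisfaction.

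The power analysis is computed "for a within-between interaction in a repeated measures ANOVA, a total sample size of 36 for three groups". Section 7 randomizes 224 subjects, 112 per arm, while section 9 says "We expect to collect data from a total of 36 subjects".

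**The concern.** Two things are open.

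**Which effect is the drug effect.** The 2 x 2 model yields Drug, Time and Drug x Time. The comparison with placebo in Hypothesis 2A rules out Time. Drug and Drug x Time both remain, and they are not interchangeable. The Drug main effect compares the average of the pre-dose and post-dose scores. The pre-dose half cannot carry a drug effect, so the contrast is diluted to half. A null Drug main effect could be read as no efficacy when Drug x Time would have detected one. If a significant result on either effect were taken as success, the 5% error rate would not hold.

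**Unused precision.** In a randomized comparison with one pre-dose and one post-dose score, ANCOVA estimates the same effect as Drug x Time. In large samples it is at least as precise, and it removes the effect of chance baseline imbalance. The plan collects what ANCOVA needs and does not use it that way.

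**Working it through.** **Inputs from the documents.** Two-sided alpha 0.05 (C.2.7); 112 per arm (section 7); total 36 in three groups, effect size 0.35, 95% power (Power Analysis). **Assumed, because not given:** pre/post correlation ρ, equal pre and post SDs (set to 1), and the raw effect d in SD units.

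**1. The plan's own power figure.** For a within-between interaction, λ = f²·N·m/(1−ρ). With f = 0.35, N = 36, m = 2 measurements and ρ = 0.5, λ = 0.1225 × 36 × 2 / 0.5 = 17.64 on 2 and 33 df. Power is 95.7%, so the stated 95% reproduces if 0.35 is Cohen's f. In a 2 x 2 design f = D/(4 SD), so the two-arm equivalent is a difference in change of D = 4 × 0.35 = 1.4 SD.

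**2. Formulas, n per arm.** The variance of the estimate is 2/n times a factor:
- Drug x Time (a t-test on change): factor 2(1−ρ), effect d, df 2n−2.
- ANCOVA: factor (1−ρ²)(1 + 1/(2n−4)), effect d, df 2n−3. The bracket is the cost of estimating the slope.
- Drug main effect: factor (1+ρ)/2, effect d/2, df 2n−2.

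Power is from the noncentral t distribution.

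**3. Choice of effect.**

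| n per arm, d, ρ | Drug main effect | Drug x Time |
|---|---|---|
| 112, 0.35, 0.5 | 32.5% | 74.1% |
| 112, 0.35, 0.8 | 28.0% | 98.5% |
| 12, 1.4, 0.5 | 47% | 91% |

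With equal SDs, the change and the average are uncorrelated. Accepting either effect as success therefore gives a type I error near 1 − 0.95² = 9.75%; simulation gave 8.8 to 9.6%.

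**4. ANCOVA against Drug x Time at 112 per arm, for scales not used for entry.**

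| ρ | Variance ratio | Change-test n per arm to match | Power, d = 0.35 | Power, d = 0.2 |
|---|---|---|---|---|
| 0.5 | 0.753 | 148.7 | 74.1 → 85.2% | 32.0 → 40.4% |
| 0.8 | 0.904 | 123.9 | 98.5 → 99.1% | 65.4 → 69.8% |
| 0.9 | 0.954 | 117.4 | both above 99.9% | 91.5 → 92.7% |

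For example, at ρ = 0.8: (0.36 × 1.00455)/0.40 = 0.904, and 112/0.904 = 123.9. The scales are repeated within a few hours, so ρ = 0.5 is an unlikely upper bound on the gain. With unequal SDs (k = post/pre), the large-sample ratio is k²(1−ρ²)/(k²+1−2kρ). It equals 1, meaning no gain, when kρ = 1, for example k = 1.25 and ρ = 0.8.

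**5. PSI.** Eligibility requires "High in PSI (PSI > 42, except for controls who should have a score < 42"). If the entry score is the pre-dose score, selection cuts its variance to v = 0.363 (top 50% kept) or 0.219 (top 20%), assuming normality. The change factor becomes (1−ρ)²v + 1−ρ², with ρ the correlation before selection. Ratios at 112 per arm for top 50% / top 20%:
- ρ = 0.5: 0.896 / 0.936
- ρ = 0.8: 0.966 / 0.981
- ρ = 0.9: 0.986 / 0.993

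For d = 0.35 and ρ = 0.5, the change test has 81% or 83% power and ANCOVA 85%.

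**6. If 36 is the intended total (12 per arm).** The ratios are 0.788, 0.945, 0.997 and 1.024 at ρ = 0.5, 0.8, 0.9 and 0.95. For PSI under the cutoff they run from 0.937 to 1.038 over ρ = 0.5 to 0.9. For D = 1.4 at ρ = 0.5, power is 91% (change) and 96% (ANCOVA); at ρ = 0.8 both exceed 99.9%.

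**The case against.** The strongest reply is that the intent can be inferred. The power analysis is for a within-between interaction, a two-group, two-time model has only one, and listing main effects and interactions is routine ANOVA wording. Nothing says the Drug main effect will be read as efficacy. This stands in part and is why the point is not called an error. But the power calculation is for three groups, names no outcome, and is a sample-size input rather than a decision rule for the two-group model.

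Second, the ANCOVA gain is small where the correlation is likely to lie. At ρ = 0.8 to 0.9 and 112 per arm, the standard error falls by only about 5% to 2%, and power for 0.35 SD is already 98.5% or more. The clearest gain at those correlations needs a 0.2 SD effect, which the documents do not mention. All of this stands.

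Third, at 12 per arm ANCOVA can lose slightly. This also stands, so the recommendation for ANCOVA applies to 112 per arm.

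Fourth, an ANCOVA for every questionnaire would absurdly take in handedness or personality. That is met by limiting it to scales scored both before and after dosing.

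**Conclusion.** The point holds as a worthwhile, low-cost improvement. The planned analysis contains a valid test, Drug x Time, but does not designate it. The alternative left open, the Drug main effect, has much less power: 28 to 33% against 74 to 98.5% for 0.35 SD at 112 per arm and ρ of 0.5 to 0.8. ANCOVA would lower the variance by about 5 to 10% at ρ of 0.8 to 0.9 for scales not used for entry, and by about 1 to 3% for PSI. The gain is larger if the correlation is nearer 0.5.

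The algebra is certain. The sizes rest on assumed correlations, effects, equal SDs and, for PSI, an assumed proportion passing the cutoff; dropout was not modelled. If 36 is the intended total, only the designation point has practical weight near ρ = 0.9.

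**What to change.** Replace the ANOVA sentence in C.2.7 with wording such as: *For each self-report scale scored both before and after dosing, the post-dose score will be compared between PREG and PBO by ANCOVA with the pre-dose score as covariate; the adjusted mean difference with its 95% confidence interval is the drug effect.*

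If the ANOVA is kept, state that Drug x Time is the treatment test and that the Drug and Time main effects are not tests of efficacy. That alone closes the designation gap. If the intended total proves to be 36, either test is acceptable.

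The cost is one or two sentences. No new data, visits or subjects are needed, and SPSS, the planned software, fits the model.
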